#### 5.9.2.2 Site Performing Correlative Study

Immunohistochemistry for PLK1 will be performed in the laboratory of [name]., at the University of Kentucky.

### 5.9.3 Systemic Inflammatory Markers

#### 5.9.3.1 Specimen(s) Receipt and Processing at the EET Biobank

Frozen plasma and PBMC samples will be accessioned and stored at -80°C until shipment to the laboratory for analysis once all timepoints for a patient are collected.

#### 5.9.3.2 Site Performing Correlative Study

Systemic inflammatory marker changes will be analyzed in the laboratory of [name], M.D., Ph.D., at the University of Kentucky.

#### 5.9.4 Immune Cells

##### 5.9.4.1 Specimen(s) Receipt and Processing at the EET Biobank

Frozen plasma and PBMC samples will be accessioned and stored at -80°C until shipment to the laboratory for analysis once all timepoints for a patient are collected.

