### 5.5.2.2 Collection of Blood in CPT Sodium Citrate Tubes for Plasma and PBMC Processing (Immune Cells and Inflammatory Markers samples)

1. Label CPT sodium citrate tubes according to the instructions in Section 5.4.2.
2. Collect three (3) 8-mL samples and gently invert to mix.
3. The samples can be stored on ice up to 2 hours before processing.
4. Centrifuge the vacutainers at 3,000 rpm (approx. 1,700 x g) at 21 C for 12 minutes so as to produce plasma. The resulting plasma should be stored in 1 ml aliquots at -80 C or below.
5. The PBMC layer should be transferred to a fresh tube with sterile PBS and centrifuged at 300 x g for 15 minutes. Repeat the washing step, then cryopreserve in 10% DMSO/FBS, preferably in 0.5 mL aliquots with 2,000,000 cells per aliquot. The samples should be frozen in a “[name]”, or similar below-freezing apparatus and stored in liquid nitrogen the next day for long term storage.
6. Ship on day of collection (whenever possible) according to instructions in Section 5.6.
7. If blood cannot be shipped on the day of collection (*e.g.*, a late scheduled collection), then refrigerate until shipment. Ship frozen plasma and mononuclear cells according to instructions in Section 5.6.

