#### Statistical Plan:

Correlative endpoints such as systemic inflammatory, immune markers, and expression of PLK and changes from pre- to post-treatment will be summarized using descriptive statistics.

Changes from baseline vs. follow-up time points will be assessed using paired test methodologies. WES data will be processed using the data processing and data analysis pipelines from the Biostatistics and Bioinformatics shared resource of Markey Cancer Center to identify candidate mutated genes with adjustment for false discovery rate.

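### PBMC storage differs between the site and Biobank instructions, and the -80°C hold is longest for the baseline sample in a single-arm paired comparison

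*Combined protocol and SAP*

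**What the plan says.** **At the site (5.5.2.2).** For plasma: "The resulting plasma should be stored in 1 ml aliquots at -80 C or below". PBMC are cryopreserved and then "stored in liquid nitrogen the next day for long term storage". Both instructions are worded as should. The same list also asks sites to "Ship on day of collection (whenever possible) according to instructions in Section 5.6". Section 5.3.2 limits shipment of processed samples to Monday through Thursday.

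**At the Biobank (5.9.3.1 and 5.9.4.1).** The two sections use the same sentence for inflammatory markers and immune cells: "Frozen plasma and PBMC samples will be accessioned and stored at -80°C until shipment to the laboratory for analysis once all timepoints" are in for that patient.

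**Samples.** Sections 5.1 and 5.8 list four CPT-tube draws: pre-treatment, Cycle 1 Week 8, Cycle 2 Week 8 (Week 16) and Week 24. All four are optional.

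**Analysis.** Objective 1.3.2 compares pre-treatment values with later ones, in percentages and absolute numbers of T-cell and myeloid suppressor subsets, and relates them to outcome. The Statistical Plan closing Section 9.5 says: "Changes from baseline vs. follow-up time points will be assessed using paired test methodologies". Section 9.3 confirms a single arm.

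The visible text sets no limit on time at -80°C, no viability or recovery check, and no rule for a patient who misses a draw.

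**The concern.** The protocol's own long-term condition for PBMC is liquid nitrogen, yet the Biobank step can keep the same cells at -80°C for months. The hold ends for all of a patient's samples together, so the earliest sample is held longest. Baseline is the reference for every paired comparison. If cells are lost at -80°C, baseline counts are depressed most and the later samples appear to rise. With no control arm handled in the same way, nothing in the planned analysis separates that rise from an effect of Sn-117m-DTPA.

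At stake is the interpretation of the immune-cell part of objective 1.3.2. Cells lost in storage cannot be recovered at the analysis stage.

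**Working it through.** The plan states no figure on this point, so there is none to reproduce.

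**1. Time at -80°C.** Assume each sample reaches the Biobank promptly and the series is released at the Week 24 draw. Hold = 24 − collection week.

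| Draw | Collection week | Weeks at -80°C |
|---|---|---|
| Pre-treatment | 0 | 24 − 0 = 24 |
| End of Cycle 1 | 8 | 24 − 8 = 16 |
| End of Cycle 2 | 16 | 24 − 16 = 8 |
| Week 24 | 24 | 24 − 24 = 0 |

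Section 11 allows baseline evaluations up to 4 weeks before treatment, which would make the first hold 24 + 4 = 28 weeks.

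**2. Link with collection time.** Within a patient, hold = constant − collection time, so the correlation is exactly −1.0. A simulation of 25 patients added a baseline 0 to 4 weeks early, visit windows of ±1 week (Section 11), and a delay of 0 to 8 weeks (the maximum in Section 7) in an assumed 30% of patients. The correlation of hold with nominal timepoint, pooled over patients, stayed between −0.98 and −0.996. Baseline holds ran from about 23 to 37 weeks.

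**3. Effect on a paired change.** Suppose, as an assumption, that log recovery falls at a constant rate λ per week. Then log(observed) = log(true) − λ × hold. The baseline hold exceeds the hold at week t by t weeks, so:

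observed log change at week t = true log change + λt.

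The bias grows in step with treatment time. Colder storage can make λ smaller. It does not remove the t.

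**4. Illustrative size.** The documents give no loss rate. The rates below are assumptions that show scale only. Time is 24 weeks × 12/52 = 5.5 months.

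| Assumed loss per month | Baseline deficit against Week 24 | Apparent rise |
|---|---|---|
| 1% | 1 − 0.99^5.5 = 5% | 1/0.946 − 1 = 6% |
| 3% | 1 − 0.97^5.5 = 15% | 1/0.846 − 1 = 18% |
| 5% | 1 − 0.95^5.5 = 25% | 1/0.754 − 1 = 33% |

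These apply to absolute numbers. A loss shared equally by all subsets leaves percentages unchanged. Percentages shift only if subsets are lost at different rates.

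**5. Incomplete series.** Let c be the chance that any one draw is obtained (assumed, equal and independent across draws). Complete series = 25c⁴. Baseline plus at least one later sample = 25c[1 − (1 − c)³].

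| c | Complete series of 25 | Usable pairs of 25 |
|---|---|---|
| 0.90 | 16.4 | 22.5 |
| 0.80 | 10.2 | 19.8 |

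The gap, about 6 to 10 patients, is what depends on how the release sentence is read.

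**The case against.** **Holding samples together has a benefit.** It allows all of a patient's samples to be assayed in one run, which keeps run-to-run variation out of the paired difference. The documents do not give this reason, but it is a good one, and the fix keeps the practice.

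**The storage times are conditional.** The site text says should, and its request for same-day shipment sits awkwardly with next-day transfer to liquid nitrogen. No maximum time at the site is given. A site that kept PBMC in liquid nitrogen and shipped late would shorten the time at -80°C. This stands: 24, 16, 8 and 0 weeks hold under prompt shipment and have not been shown for every patient.

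**Temperature is not the source of the confounding.** A reader might infer that the mismatch makes storage time mirror treatment time. It does not: the hold until the last draw does that, and liquid nitrogen would leave the same mirror. Temperature bears only on how large a storage effect could be.

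**Incomplete series are not said to be withheld.** A reader might infer that a patient who misses a draw has nothing analysed. The text does not say so. Since every draw is optional, the sentence can mean all the timepoints that the patient provides, and nothing orders incomplete series held back or discarded. Nor does progression clearly cancel the Week 24 draw: Section 6.4 ends treatment, while Section 6.5 continues follow-up, although footnote a of the calendar is ambiguous. Text directly after 5.9.3.2 and 5.9.4.2 was not available for this review, so a release rule may exist there.

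**Plasma is consistent.** Site and Biobank agree on -80°C for plasma, so the temperature conflict concerns PBMC only.

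**Conclusion.** The point holds as a minor one. The protocol gives two conditions for keeping PBMC over months, and they should be reconciled. With prompt shipment, baseline PBMC spend about 24 weeks at -80°C and Week 24 PBMC almost none. Any loss would therefore line up with treatment time, and a single-arm paired test could not detect or remove it.

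Whether there is a material loss is unknown. The 5% to 25% deficits rest on assumed monthly rates and a constant-rate model, and concern absolute numbers. The documents do not support a claim that the results will be biased by any stated amount.

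The release of incomplete series is a gap in wording. The 6 to 10 patients computed above would be lost only under the strictest reading and the assumed collection rates.

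The assays are optional and exploratory, in at most 25 patients. The primary endpoint, sample size and stopping rules are untouched.

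**What to change.** In 5.9.3.1 and 5.9.4.1:

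- Keep plasma at -80°C. Store PBMC in liquid nitrogen from receipt until shipment, in line with 5.5.2.2.
- Keep assaying all of a patient's samples in one run.
- Record, for each sample, the storage time and the post-thaw viability and recovery. Liquid nitrogen leaves storage time collinear with collection time, so these records are needed to judge whether storage could explain an apparent change.
- State that a patient's samples are released once his last obtainable sample has arrived or he is off study.

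In the Section 9.5 Statistical Plan, say that every patient with a baseline and at least one later sample enters the paired analysis.

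The cost is wording, routine recording at thaw, and liquid-nitrogen space for at most 4 timepoints × 25 patients = 100 patient-timepoints. No new samples or visits are needed.

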##### 5.9.4.2 Site Performing Correlative Study

Immune cell population changes will be analyzed in the laboratory of [name], M.D., Ph.D., at the University of Kentucky.

### 5.10 Special Studies

#### 5.10.1 Sn-117m-DTPA Dosimetry

##### 5.10.1.1 Outcome Measure

Sn-117m-DTPA activity will be evaluated as a primary correlative of radioactivity distribution. Tin is an avid bone seeker, and its biodistribution is nearly identical to that of Tc-99m-MDP (Swailem *et al.*, 1998). The highest tin distribution is seen in bone surfaces (82%) with increased uptake in bone metastases. Other normal physiological tissue retention can be seen in liver, lungs, spleen, heart, and kidneys, and their uptake varies with the rates of clearance.

##### 5.10.1.2 Assessment

##### 5.10.1.2.1 Method of Assessment

Sn-117m-DTPA activity will be assessed by gamma camera dosimetry outlined here and in

Appendix J. A positive Sn-117m-DTPA scan is defined as tumor uptake  $\geq$  normal liver uptake observed on planar imaging. Focal and heterogeneous Sn-117m-DTPA bone uptake will be correlated with the baseline Tc-99m-MDP dosimetry results.

#### 5.10.1.2.2 Timing of Assessment

Serial whole-body (head to mid-thigh) planar images in the anterior and posterior projections will be acquired during the first cycle only, 1 hour, 4 hours (or within 4-6 hours), 24 hours (or within 16-24 hours), 48 hours (or within 40-48 hours), 72 hours (or within 60-72 hours), 1 week ( $\pm 2$  days), and 4 weeks ( $\pm 2$  days) after the first Sn-117m-DTPA dose (see the table below). If one or more images are not performed at the correct time, make-up whole-body scans are not needed, especially for patients that live in the vicinity of the clinic.

Table: Dosimetry image acquisition timelines

Timing (Target range)	Imaging
1 hr	Whole body scan *
4 hrs (4-6 hrs)	Whole body scan
24 hrs (16-24 hrs)	Whole body scan + SPECT/CT
48 hrs (40-48 hrs)	Whole body scan + SPECT/CT
72 hr (60-72 hrs)	Whole body scan
1 week ( $\pm 2$ days)	Whole body scan
4 weeks ( $\pm 2$ days)	Whole body scan

\*No voiding between radiopharmaceutical infusion and 1st imaging.

SPECT/CT: single-photon emission computed tomography/computed tomography

#### Dosimetry reference standard preparation and utilization

After each therapeutic session, the residual activity in the vial will be measured in a dose calibrator, labelled as a reference standard, and kept for further imaging. The reference standard will be placed at the inferior part within the field of view of whole-body scans at all time points. Caution will be taken for the standard reference not to touch the patient during imaging. Optional 3D SPECT scans will be performed at 24 hours and 48 hours in the upper abdomen to include kidneys, liver, and spleen. Extending coverage can be done to include regions determined by the planar imaging.

#### 5.10.1.3 Data Recording

##### 5.10.1.3.1 Method of Recording

We will compare radiopharmaceutical whole-body retention rates of our patients to the previously reported values. Image based dosimetry analysis will be performed.

- 1) Equipment: Large-field-of-view dual-head gamma camera will be used.
- 2) Energy window: 20% window centered at 159 KeV
- 3) Collimator: Low-energy high-resolution parallel-hole (LHRP) collimator

### Image Analysis:

Geometric mean will be calculated from anterior and posterior images for both whole-body. Counts in whole-body images will be normalized at the first image, scanning the patient with 100% of the injected activity at 1 hour before patient void or by subtracting the percent of injected activity eliminated in the urine before the first image acquisition.

Patient-specific organ mass (liver, spleen, and kidneys) will be obtained by measuring organ volume using CT scan and assuming liver, spleen, and kidney density as 1.03 g/cc. Regions of interest (ROIs) will be placed over whole body, liver, spleen, and kidneys, as well as the dosimetry reference standard on both anterior and posterior planar whole body images. Both total counts and number of pixels will be recorded for each ROI. Target organ radiation absorbed dose will be calculated using the MIRD schema or related methodology.

#### 5.10.1.3.2 Timing of Recording

Dosimetry scans will be assessed within one week of Sn-117m-DTPA administration.

### 5.10.2 Sn-117m-DTPA Palliative Pain Effect

#### 5.10.2.1 Outcome Measure

The effect of Sn-117m-DTPA treatment on cancer-related bone pain will be assessed via patient reports of pain intensity and changes in analgesic use to manage pain. Patients will be asked to complete the BPI-SF questionnaire, which rates several aspects of pain and the effects of pain on common activities, on an 11-point scale; a “0” represents “no pain/no pain relief/does not interfere”, and an “11” represents “pain as bad as you can imagine/complete relief/completely interferes”. Patients will also be asked to complete a simple analgesic use log by choosing among the options of “decreased”, “stable”, or “increased” use of any pain medication.

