#### Classification of pain index based on diary pain intensity rating and analgesic intake

Pain response	Pain index	Diary pain rating change from baseline	Analgesic intake compared with baseline
Complete	1	Decrease $\geq 90\%$	Stable or reduced
Marked	2	Decrease $\geq 50\%$ to $< 90\%$	Stable or reduced
Moderate	3	Decrease $> 33\%$ to $< 50\%$	Stable or reduced
Minimal	4	Decrease $\geq 20\%$ or increase $< 33\%$	Stable
None	5	Decrease $< 20\%$ or increase $> 33\%$	Stable

Pain progression	6	Increase $\geq 20\%$	Stable or increased
		Decrease $<20\%$ or increase $<20\%$	Increased
		Decrease $\geq 20\%$	Increased

This pain index is derived from a combination of the following 11-point pain intensity scale and analgesic consumption categorized according to the World Health Organization (WHO) analgesic ladder.

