### 5.10.2.2.2 Timing of Assessment

Pain at baseline and analgesic use (pre-treatment, Week 0) will be measured via serial (daily) assessments in a 7-day run-in period. Patients will be considered evaluable if they complete assessments on  $\geq 4$  days within the 7-day run-in period. During treatment, pain and analgesic use will be measured every 2 weeks through Week 28, followed by routine clinic follow-up until 1 year or when patients experience new pain. Complete pain assessments via the full BPI-SF (Appendix D) will be collected at baseline, after Cycle 1, after Cycle 2, and at Week 28. Pain assessments will be halted at the patient's request or if the patient discontinues study treatment for reasons other than disease progression.

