A: Sn-117m-DTPA: 20 mCi/70 kg (0.28 mCi/kg) slow IV injection over 10 min on C1D1 and C2D1

\*Patients can be retreated if pain recurs within 6 months after 16-week pain observation period

a: Follow-up visit evaluation. Every 3 months or as clinically indicated up to one year from the first dose injection or disease progression

b: Albumin, ALP, total bilirubin, bicarbonate, BUN, calcium, chloride, creatinine, glucose, LDH, sodium, potassium, total protein, SGOT [AST], SGPT [ALT].

c: Pre-treatment daily baseline pain and analgesic use for 7 days (at least 4 out of 7 days) is required before treatment initiation. Patients will be asked to report their pain at its worst in the last 24 hours and analgesic use (stable/reduced/increased) by digital version every 2 weeks through Week 28, followed by routine clinic follow up or when they experience new pain during off-visit. **A full short version of brief pain inventory (BPI) will be asked at baseline, after Cycle 1, after Cycle 2, and at Week 24.**

d: PRO-CTCAE survey items will be assessed by digital instruments. Beginning at Week 28, surveys are requested every 3 months for 6 months after the last study treatment administration.

e: Serial DTPA dosimetry scans (optional) will be obtained at 1 hour, 4 hours (or within 4-6 hours), 24 hours (or within 16-24 hours), 48 hours (or within 36-48 hours), 72 hours (or within 60-72 hours), 1 week (+/2 days), and 4 weeks (+/2 days) post-infusion. The dosimetry scan will only be performed with first cycle of injection.

f: Urine collection for urinalysis will be collected at the indicated time points or as clinically indicated to monitor for microscopic or macroscopic hematuria as part of genitourinary toxicity monitoring.

g: Imaging: Follow up tumor response will be evaluated by CT scan of abdomen and pelvis, bone scan and chest X-ray. If Chest X-ray shows abnormal or clinically symptomatic, then CT chest should be obtained. Follow-up scans at every 8 weeks will be performed as clinically indicated, per institutional standards. PSMA PET CT scan at baseline is also acceptable.

*NCI Protocol #: 10437*

*Version Date: January 10, 2022*

h: Blood collections for research during Cycles 1 and 2 should be collected on the last day of each cycle.

i: CBC and serum chemistry should be performed 1 week before the start of Cycle 2.

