\*\* Study coordinator/research nurse will require to ask pain medications list including names, dosage and frequency and also is required to fill out pain medication list form during every clinic visit.

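### The pain index needs analgesic intake against baseline on the WHO ladder; the patient log named for it gives no amount and no visible reference point, and no rule links the verified medication list to the index

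*Combined protocol and SAP*

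**What the plan says.** The table in Section 5.10.2.2.1 defines the index from two components: change in pain rating from baseline, and a column headed "Analgesic intake compared with baseline". Index 1 to 3 requires stable or reduced intake. Every row with increased intake scores 6, even where pain has fallen by 20% or more. Under the table, the second component is described as "analgesic consumption categorized according to the World Health Organization (WHO) analgesic ladder".

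For data collection, Section 5.10.2.1 says: "Patients will also be asked to complete a simple analgesic use log", with the options decreased, stable or increased. The log reproduced under Analgesic Use/Consumption shows only the three option headings. Study Calendar note c gives pain a 24-hour recall period but describes the other item as "analgesic use (stable/reduced/increased) by digital version every 2 weeks through Week 28", with no comparator. Section 5.10.2.3.1 names the pain assessments and the analgesic logs as the data to be post-processed.

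On timing, Section 5.10.2.2.2 says "Pain at baseline and analgesic use (pre-treatment, Week 0) will be measured via serial (daily) assessments in a 7-day run-in period", and then "During treatment, pain and analgesic use will be measured every 2 weeks through Week 28".

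There is a second source. The coordinator asks for drug names, dosage and frequency and "is required to fill out pain medication list form during every clinic visit" (Study Calendar, double-asterisk note; form in Appendix F). The calendar schedules this pre-study and at most later visits. Section 6.3.2 places no restriction on analgesics.

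**The concern.** The analgesic category decides response: with the same fall in pain, stable gives index 3 or below and increased gives 6. The index asks for a level on the WHO ladder compared with baseline. The log supplies a direction of change without a level, and its comparator is not visible. A patient who raised his opioid dose early and then kept it constant could truthfully answer stable at every later report.

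The trial is single-arm and open-label (Section 9.1), so no control group would share the error. False credit would be attributed to the study drug. The overall pain response rate (Section 9.4.4) and the duration of pain response (Section 9.4.5) use the same index and would inherit the problem.

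**Working it through.** **1. Required against collected**

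| Item | Index table (5.10.2.2.1) | Patient log (5.10.2.1, calendar note c) | Medication list (calendar, Appendix F) |
|---|---|---|---|
| Comparator | Baseline | None visible | Pre-study list exists |
| Scale | WHO ladder | Three directions | Drug, dose, frequency |
| Role in index | – | Named for post-processing (5.10.2.3.1) | None stated |

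The calendar schedules the log at Weeks 2, 4, …, 28, which is 14 reports. The list is scheduled at all of these except Weeks 18, 22 and 26, so at 11 of 14.

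**2. Same patient, two readings of the log (assumed values)**

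False credit. Baseline pain is 6. The opioid is stepped up at Week 4 and then held. Pain is 3 from Week 6, a fall of (6 − 3)/6 = 50%.
- Against baseline: increased at every visit from Week 4, so index 6 throughout. Non-responder.
- Against the previous report: index 6 at Week 4 only, then stable with a 50% fall, so index 2 from Week 6 to Week 28. Index 3 or below is reached by Week 12 and held for 16 weeks (Weeks 6 to 22). Responder.

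False failure. Baseline pain is 6, and pain is 3 from Week 2. Analgesics are reduced at Weeks 6 to 12 and return to the baseline amount at Week 14.
- Against baseline: stable or reduced throughout, index 2. Responder.
- Against the previous report: increased at Week 14, index 6. Every 16-week window starting by Week 12 contains Week 14. Non-responder.

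False credit needs the increase to come before the first index of 3 or below. An increase reported inside the 16-week window scores 6 on either reading.

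**3. Effect on the decision rule**

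Inputs from Section 9.1: 25 patients, stop at 1 or fewer in stage 1, fail at 5 or fewer in total, null rate 10%, alternative 30%. With stage-1 size n1 and response probability p:

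P(success) = sum over x from 2 to n1 of Bin(x; n1, p) × P[Bin(25 − n1, p) ≥ 6 − x].

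The plan's own figures first. At n1 = 10 and p = 0.10, the terms for x = 2, 3, 4, 5 and 6 or more are 0.0108 + 0.0106 + 0.0050 + 0.0012 + 0.0001 = 0.0277. Power at p = 0.30 is 74.0% and early stopping under the null is 73.6%. These do not match the stated 3.28%, 80.17% and about 55%. With n1 = 15 the results are 3.28%, 80.17% and 54.9%, which do match. That mismatch in stage sizes is a separate matter, so both versions are shown.

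If a share f of true non-responders is falsely credited, the apparent null rate is q = 0.10 + 0.90 f. The documents give no value for f.

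| f (assumed) | q | False-positive rate, 10+15 | False-positive rate, 15+10 |
|---|---|---|---|
| 0 | 10% | 2.8% | 3.3% |
| 1.1% | 11% | 4.2% | 4.9% |
| 2% | 11.8% | 5.5% | 6.5% |
| 5.6% | 15% | 13.7% | 15.9% |

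One misclassified patient changes the observed rate by 1/25 = 4 percentage points.

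**The case against.** The strongest reply is that the plan already states the anchor. The index column is headed by a comparison with baseline, and rows with increased intake score 6, so crediting relief obtained through more analgesics is excluded by definition. A visit-to-visit reading contradicts the table and could arise only from how patients understand the form. This stands as far as it goes: the definition is sound. What is missing is a way of getting from the data named for the index to that definition.

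A reader might also infer several stronger points that the documents do not support:

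- **That no baseline level of analgesic use exists.** It does: the medication list is scheduled pre-study with drug, dose and frequency. The gap is a missing derivation rule, not missing data.
- **That the run-in itself is recorded as decreased, stable or increased.** The run-in response options are not stated. Note c attaches the three options to the two-weekly reports.
- **That the log is definitely un-anchored.** The body of the Appendix E form and the app screens are not visible in the text available, so a reference period there cannot be ruled out. An anchor alone would still not supply a WHO step or say which source governs.
- **That the response rate will be inflated.** The second example in the working shows a false failure by the same mechanism.
- **That the false-positive rate is about 14% to 16%.** That rests on one assumed value of f. At an apparent null rate of 11% the rule stays below 5% in both stage orders.

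**Conclusion.** The concern holds as a gap in how the endpoint is derived. The index requires intake against baseline on the WHO ladder. The log named for it cannot be mapped to a WHO step and shows no reference point in the available text. The list that could supply both is not linked to the index. Following the log can therefore give a wrong responder status in either direction. The net direction is unknown, but false credit is the more serious risk in an uncontrolled trial because it favours a false positive conclusion.

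The size cannot be fixed from the documents. It depends on how patients interpret the log and on how often analgesics change before first response. As a sensitivity range, false credit to 2% of true non-responders is enough to take the false-positive rate above the 5% design level (5.5% or 6.5%). The point should be settled before the primary endpoint is scored; it does not alter the sample size or the decision bounds.

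**What to change.** 1. State in Section 5.10.2.2.1, and cross-refer from Section 9.1, that the analgesic category at each assessment is derived from the coordinator-verified medication list against the pre-treatment list.
2. Pre-specify one scoring rule consistent with the WHO ladder named under the index table, including how a dose change within a ladder step is classified.
3. Anchor the log wording, in the app and in Appendix E, to the week before the first injection.
4. Use the log alone only at Weeks 18, 22 and 26, where no list is scheduled.

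Cost: no new visits, instruments or patients. A scoring rule has to be written, including how intake is compared when a patient changes from one analgesic to another, and one item on the form and in the app has to be reworded.
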